**Patients who are off protocol therapy must be followed until an “Off Study Criterion” is met.**

#### 6.4.2.1 *Data Submission Schedule for Patients Off Treatment*

All patients must be followed for a minimum of 30 days from the last treatment date. Toxicities that are considered at least possibly related to study treatment and are ongoing at the end of day 30 of last treatment date will be followed until resolution or return to baseline, unless consent is withdrawn for further data submission or follow-up.

Patients who do not meet an off-study criterion will continue to be followed for 2 years from the last dose of protocol treatment for the monitoring of unexpected later developing toxicities or other morbidity and to document disease progression and survival. Data should be updated quarterly in the RAVE database. The requested follow-up data, including imaging uploads requested in [Section 5.4](#), are to be submitted quarterly in the RAVE database from the date the patient went off treatment. Data to be recorded during this interval are the following:

- Any adverse events that are possibly, probably, or definitely related to the study drug (see [Section 10](#) for specific reporting timelines)
- Dates of disease assessment and results of the associated disease assessments.
- Date of disease progression
- Date of commencement of new anticancer therapy
- Date of most recent contact
- Date of death

#### 6.4.3 Criteria for Removal from Study

Patients who are off protocol therapy will be followed until they meet criteria for removal from study. The date and reason for the patient coming off study must be documented in the eCRF and the Operations, Biostatistics and Data Management Core (OBDMC) must be notified according to standard reporting guidelines (see [Sections 10.3, 10.4](#), and [13.2](#), Data submission for Off Study, and the Required Data and Timetable Submission from located on the PBTC-056 Protocol Webpage).

Ongoing AEs, or AEs that emerge after the patient is removed from protocol therapy but within 30 days of the last dose of study treatment, must be followed and reported via Rave and CTEP-AERS (if applicable). Toxicities that are at least possibly related to the study treatment and are ongoing at the end of day 30 of last treatment date will be followed until resolution or return to baseline, whichever is longer.

- Patient determined to be ineligible.
  - If the patient was found to be ineligible after starting treatment, follow-up should continue for 30 days from the last administration of study drug or until any drug-related toxicity resolves or returns to baseline, whichever is longer.
- Patient did not initiate treatment on study.
- Parent, patient, or guardian withdraws consent for further required observations of data submission.
- Patient death while on study. The IRB, Study Chair, and OBDMC must be notified as per [Section 10.3](#).
- Patient has started another anti-cancer therapy. Follow-up must still be completed for 30 days following the last treatment date.
- Patient has completed study follow-up which is defined as 2 years following last dose of INCB007839.
- Progressive disease
  - If PD occurs within less than 30 days of off-treatment date, then follow-up should continue until 30 days from off-treatment date.
  - If the off-treatment reason is toxicity and the patient is subsequently found to have PD, then follow-up should continue for 30 days from the off-treatment date or until the toxicity resolves or returns to baseline, whichever is longer.

#### 6.4.3.1 *Data Submission for Patients Off study*

No data will be collected documenting treatment or reporting events or disease status that occur subsequent to the official “off study” date with the exception of adverse events with an attribution of possible, probable, or definite that occur after the “off study” date.

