### 1.2 Secondary Objectives

- 1.2.1 To make a preliminary assessment of efficacy via objective response and overall survival in children with recurrent/progressive high-grade glioma.

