#### 6.1.1 INCB007839

INCB007839 is supplied as 100 mg sustained release tablets. Patients will receive INCB007839 orally twice a day each day for 28-day cycles. Patients may continue to receive INCB007839 on study for up to 26 courses (approximately 2 years) in the absence of disease progression or unacceptable toxicity. Enrolled patients will be followed after completion of study therapy for 2 years or death, whichever occurs first. Delays between courses for reasons other than toxicity may occasionally occur, however, dosing should follow the treatment plan as closely as possible. Discuss and document any protocol deviations with the Study Chair. Duration of therapy is defined in [Section 6.4](#).

Dosing should be adjusted based on body surface area (BSA) calculated at the beginning of each course of therapy. The dose prescribed should be rounded to the nearest deliverable dose based on the BSA adjustment and the available pill size. Dosing tables which reflect this approach are available in [Appendix B](#). Patients will be provided with a medication diary for INCB007839, instructed in its use, and must bring the diary as well as the remaining pill bottles with them to each appointment. The medication diary is in [Appendix C](#).

As much as possible, INCB007839 should be taken without food (1 hour before meals or 2 hours after), with water rather than other fluids. Dosing is every 12 hours ( $\pm$  2 hours), but if a dose is not given within 4 hours, consider it missed. If a dose is missed, it should be documented in the diary and the next scheduled dose should be taken as scheduled. Patients who vomit a dose of INCB007839 should NOT be re-dosed, and appropriate anti-emetic therapy should be implemented prior to the next scheduled dose.

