#### 6.4.2 Off Treatment Criteria

At the discontinuation of treatment, the "Off Treatment Date" is to be recorded in the eCRF and is to be consistent with the reason given for going off treatment. The "Last Treatment Date" is defined as the last date that the patient received protocol based therapy. The reason for discontinuation of treatment must be documented by the attending investigator in the medical record and recorded in the eCRF.

Patients will be considered Off Treatment for the following reasons:

- Development of unacceptable toxicity as outlined in [Section 6.2](#). See [Section 10.3](#) and [10.4](#) for specific reporting requirements.
- Progressive disease (PD) as described in [Section 12.2](#).
- Development of a medical or psychiatric illness that in the investigator's judgment renders the patient incapable of further therapy on this protocol or the treating physician determines continuation on this study is not in the patient's best interest.
- The patient, parent, or legal guardian refuses further treatment on this protocol. In this case the investigator should clarify if the family also wishes to withdraw consent for continued participation for data collection purposes.
- Completion of all protocol defined treatment
- Pregnancy
- Non-Compliance that in the opinion of the investigator does not allow for ongoing participation.

- Termination of the study by the sponsor
- Investigational agent manufacturer can no longer provide the study agent.
- Development of a non-central line related thrombosis

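### Overall survival is a secondary objective, but the off-study rules end data collection about 30 days after progression, so most tumor deaths may go unrecorded

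*Combined protocol and SAP*

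**What the plan says.** - **Objective (1.2.1):** "To make a preliminary assessment of efficacy via objective response and overall survival in children with recurrent/progressive high-grade glioma".
- **General follow-up statement (6.1.1):** "Enrolled patients will be followed after completion of study therapy for 2 years or death, whichever occurs first". It makes no exception for progression or new therapy.
- **Off treatment (6.4.2):** the listed reasons include "Progressive disease (PD) as described in" Section 12.2.
- **Follow-up after treatment (6.4.2.1):** "Patients who do not meet an off-study criterion will continue to be followed for 2 years from the last dose of protocol treatment". The stated purpose is "monitoring of unexpected later developing toxicities or other morbidity and to document disease progression and survival". Date of death and date of most recent contact are among the fields updated quarterly.
- **Off study (6.4.3):** progressive disease is a criterion, with this minimum: "If PD occurs within less than 30 days of off-treatment date, then follow-up should continue until 30 days from off-treatment date". New therapy is another: "Patient has started another anti-cancer therapy. Follow-up must still be completed for 30 days following the last treatment date". Unresolved toxicity can extend follow-up.
- **After off study (6.4.3.1):** "No data will be collected documenting treatment or reporting events or disease status that occur subsequent to the official" off-study date. The one exception is adverse events with possible, probable or definite attribution.
- **Expedited reporting (10.3.3 and its footnote 1):** a death from any cause is reportable up to 30 days after the last dose. Later Grade 5 events are reportable only if at least possibly related.
- **Definition and analysis:** 12.2 defines progression-free survival but not OS. Section 9.3 says responses will be described and does not mention OS.

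**The concern.** OS needs a death date or a last-contact date that does not depend on disease status. Here the survival follow-up in 6.4.2.1 is reserved for patients who have met no off-study criterion, and progression is itself such a criterion. Section 2.1.1 states that no effective treatment exists at recurrence or progression and that most children eventually die of the disease. Most deaths would therefore be expected after progression, when collection has stopped.

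A patient censored shortly after progression has a much higher risk of death than patients still under observation. Kaplan-Meier estimation assumes the opposite, that censored patients have the same prognosis as those remaining at risk, so its OS estimate would be too high. The OS half of 1.2.1 is at stake. Safety, dose finding, pharmacokinetics and objective response are not.

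**Working it through.** **Step 1. Trace one patient through the text.** A patient treated until progression goes off treatment at progression (6.4.2) and meets an off-study criterion at the same time (6.4.3). The minimum then holds the patient on study until 30 days after the off-treatment date. After that, only at least possibly related adverse events are collected (6.4.3.1). A death from tumor on, say, day 60 after progression is outside 6.4.2.1 because the patient is off study. It is outside 6.4.3.1 because it is not attributed to the drug. It is outside 10.3.3 because it falls more than 30 days after the last dose. No section provides survival-only follow-up. A patient already off treatment for 30 days or more when progression occurs goes off study at progression, unless unresolved toxicity extends follow-up.

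**Step 2. Illustrate the size.** The plan has no OS figure to reproduce. From the documents: the 30-day minimum, 2 years from last dose, a maximum of about 28 patients, and 15 if Dose Level 1 is safe (9.2.1). Assumed, not in the documents:

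- exponential times;
- median time to first event 2, 3 or 4 months;
- median post-progression survival m = 1, 2, 3, 4 or 6 months;
- a share f = 5% or 10% dying without progression;
- a share q already off treatment for at least 30 days at progression, 0 or 20%.

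This gives 3 × 5 × 2 = 30 scenarios for each q.

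Share of deaths recorded = f + (1 − f)(1 − q)(1 − 2^(−g/m)), with g = 30/30.4375 = 0.986 month.

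For q = 0, m = 1, f = 5%: 0.05 + 0.95 × (1 − 2^(−0.986)) = 0.05 + 0.95 × 0.495 = 0.520.

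| m (months) | f = 5% | f = 10% |
|---|---|---|
| 1 | 0.520 | 0.545 |
| 2 | 0.325 | 0.360 |
| 3 | 0.243 | 0.283 |
| 4 | 0.199 | 0.241 |
| 6 | 0.152 | 0.197 |

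The extremes are 28 × 0.152 = 4.3 to 28 × 0.545 = 15.3 deaths of 28, or 15 × 0.152 = 2.3 to 15 × 0.545 = 8.2 of 15. With q = 20% the range is 0.132 to 0.456.

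**Step 3. Same calculation with vital status kept for 2 years after last dose** (g = 24, last dose at progression). At m = 6, f = 5%: 0.05 + 0.95 × (1 − 2^(−4)) = 0.941, and at m = 1 it is 1.000. That is 26.3 to 28.0 of 28.

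**Step 4. Effect on a Kaplan-Meier estimate censored at off-study (q = 0).** With 400,000 simulated patients per scenario, true 6-month OS was 22-77% and the estimate was too high by about 9-20 percentage points. With 20,000 simulated trials of 28 patients per scenario, the sampling SD of 6-month OS was 8-14 points. The Kaplan-Meier median was reached in about 99% of trials at m = 1, 79-88% at m = 2, 58-72% at m = 3, 44-61% at m = 4 and 30-47% at m = 6. With follow-up as in Step 3, the 6-month bias is zero.

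Loss to follow-up, new therapy before progression and extension for toxicity were not modelled.

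**The case against.** Five points can be made for the plan.

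1. **No real contradiction.** Section 6.4 is the operative text and may simply qualify the one sentence in 6.1.1, which speaks of completing therapy. That is a fair reading. It removes the conflict, but patients who progress still have no survival follow-up and the OS objective still cannot be met.
2. **Vital status is not named in 6.4.3.1.** This is true, but events most naturally include death, and 6.4.2.1 confines the date-of-death field to the follow-up interval. The data timetable on the protocol webpage is not in the documents and may add detail. It should not have to override an explicit rule.
3. **Low stakes.** OS here is preliminary and uncontrolled, in a phase 1 trial, and no Kaplan-Meier analysis is planned. The efficacy-evaluable definition in 12.1 is tied to the tumor response criteria and does not set up an OS population. All of this stands and limits the consequence. Descriptive reporting still cannot recover death dates that were never collected.
4. **The figures rest on assumptions.** They do, and the range is wide. In particular, failure to reach the median is a serious problem mainly when post-progression survival is about 3 months or longer. The finding depends on the text, not on these figures.
5. **Cost.** Contact after progression may need consent wording. The consent pages were removed, so this cannot be checked.

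**Conclusion.** The concern holds, with high confidence, and should be fixed. Followed exactly, the plan does not collect tumor deaths after off-study, so the OS part of 1.2.1 would rest on informatively censored data, biased upward. Under the assumed medians, roughly 15-55% of deaths would be recorded, against 94-100% with 2-year vital status. The 6-month bias of about 9-20 points is of the same order as, or larger than, the sampling SD with 28 patients. These numbers are an illustration and not bounds. The missing OS definition and analysis statement are a minor, related gap.

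**What to change.** Reconcile 6.1.1, 6.4.2.1, 6.4.3 and 6.4.3.1 so that vital status (date of death or last contact) is collected quarterly after progression or new anti-cancer therapy, until 2 years after the last dose, death, or withdrawal of consent. In 12.2, define OS as the time from first dose to death from any cause, censored at last contact. In 9.3, state that it is reported descriptively.

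The amendment is small. The fields and the quarterly schedule already exist in 6.4.2.1. The added burden is at most about 28 patients × 8 quarterly contacts = 224, and fewer because contacts stop at death. Check whether the consent form already covers this contact.

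If the sponsor prefers to keep the off-study rule, remove OS from 1.2.1 and align 6.1.1 with 6.4.2.1. That needs text changes only. Neither option touches dosing or treatment rules.

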## 7.0 DOSING DELAYS/DOSE MODIFICATIONS

The Study Chair or Co-Chair must be notified of any dosage modifications, prior to the implementation of the dose modification. There is only one dose reduction planned for this study. Patients receiving INCB007839 80 mg/m^2 BID daily and who meet criteria for a dose reduction must be removed from protocol therapy.

### 7.1 Hematologic and Non-hematologic Adverse Events and Management

#### 7.1.1 Dose Modification for Thromboembolic Toxicity

Thromboembolic event *	Management
Grade 1	Manage superficial thrombosis as per institutional standards, no change in dose needed.
Grade 2 **	Thromboembolic events should be managed as per institutional standards. Unless thrombosis is catheter-associated, discontinue INCB007839. If catheter-associated, hold INCB007839 until catheter-associated thrombosis is resolved.
Grade 3	Thromboembolic events should be managed as per institutional

Thromboembolic event *	Management
	standards. Discontinue INCB007839.
Grade 4	Thromboembolic events should be managed as per institutional standards. Discontinue INCB007839.
* Patients requiring a delay of > 14 days should go off protocol therapy.	
** Please note: Grade 2 superficial thrombophlebitis should be considered a Grade 1 thromboembolic event and managed as per the Grade 1 management above.	

### 7.1.2 Dose Modification for Non-thromboembolic Toxicity

A patient who has a non-thromboembolic toxicity at 120 mg/m^2 or is delayed > 7 days from the planned start of the next course should be dose reduced to 80 mg/m^2 on subsequent cycles. A patient who has a non-thromboembolic toxicity at 80 mg/m^2 or is delayed > 7 days from the planned start the next course will not receive further treatment on study and will be considered off treatment (see [Section 6.4.2](#)).

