## 6.2 Definition of Dose-Limiting Toxicity (DLT)

DLT will be defined as any of the events listed in this section that are at least possibly related to the investigational agent and that occur during the dose-finding period regardless of expectedness.

- Any INCB007839-related adverse event during the first course of therapy that leads to a dose reduction or results in the permanent cessation of therapy will be considered dose limiting. All dose modifications in all courses are to follow the guidelines provided.
- Any INCB007839-related adverse event during the first course of therapy that results in a delay of treatment > 7 days.

6.2.1 Non-hematologic dose limiting toxicity is defined as:

- Any Grade 4 non-hematologic toxicity
- Any Grade 3 non-hematologic toxicity with the exception of:
  - Grade 3 nausea and vomiting of < 5 days and responsive to anti-emetic treatment
  - Grade 3 elevation of transaminases that returns to levels meeting eligibility criteria within 7 days of study drug interruption and does not recur upon restarting drug.
  - Grade 3 fever or infection of fewer than 5 days in duration
  - Grade 3 hypophosphatemia, hypokalemia, hypocalcemia, or hypomagnesemia responsive to oral supplementation
- Any Grade 2 non-hematologic toxicity that persists for > 7 days and is considered medically significant or sufficiently intolerable by the patient that the toxicity requires treatment interruption
- Any deep venous thrombotic event (superficial phlebitis is excluded unless Grade 3 or 4 as above)
  - If a patient on this study has a thrombotic/thromboembolic event that is not related to the central line, treatment with INCB007839 will be discontinued and not restarted. Determination of attribution will be reviewed by the study team and discussed with PBTC Toxicity Committee and CTEP; and such events will be reported to the CTEP-AERS, PBTC DSMB, and the FDA as events of special interest in an expedited fashion. See special reporting requirements in [Section 10.3](#). In this event, enrollment will be halted until fully reviewed. In addition, any patient experiencing a non-central line-related thromboembolic event should have the

studies listed below performed as soon as possible after the event.

- Patients with a venous thrombosis should have the following assessed as soon as possible after thrombosis is suspected/confirmed:
  - CBC
  - Antithrombin
  - Protein C
  - Protein S
  - Factor V Leiden
  - Prothrombin G20210A gene analysis

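### Section 7.1.2 sets no threshold for dose reduction; read literally with Section 6.2, it makes low-grade and exempted Course 1 toxicities dose limiting

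*Combined protocol and SAP*

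**What the plan says.** Section 7.1.2 opens with "A patient who has a non-thromboembolic toxicity at 120 mg/m"² and reduces that child to 80 mg/m² "on subsequent cycles. A patient who has a non-thromboembolic toxicity at 80 mg/m"², who then goes off treatment. A delay of more than 7 days in starting the next course is a separate trigger with the same consequences. No grade, duration, attribution or exemption is attached to the word toxicity. The parent heading, "7.1 Hematologic and Non-hematologic Adverse Events and Management", brings blood counts into scope.

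The parallel rule for clots, 7.1.1, is graded. For Grade 1 it says "Manage superficial thrombosis as per institutional standards, no change in dose needed".

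Section 6.2 confines DLTs to events at least possibly related to the drug in the dose-finding period. Its first bullet makes dose limiting "Any INCB007839-related adverse event during the first course of therapy that leads to a dose reduction or results in the permanent cessation of therapy", and adds that dose changes in every course follow the protocol's guidelines. Its second bullet adds a related Course 1 event that delays treatment by more than 7 days.

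Section 6.2.1 exempts four kinds of Grade 3 event:

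- "Grade 3 nausea and vomiting of < 5 days and responsive to anti-emetic treatment"
- a transaminase rise that "returns to levels meeting eligibility criteria within 7 days of study drug interruption and does not recur upon restarting drug"
- a febrile or infectious episode lasting under 5 days
- low phosphate, potassium, calcium or magnesium corrected by oral supplements

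Section 6.2.2 exempts Grade 4 lymphopenia.

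Under 6.2.4 and 9.1, more than one DLT in the first six children at 120 mg/m² stops enrollment there and moves the trial to 80 mg/m².

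**The concern.** The dose-modification rule feeds the DLT definition, and it is wider than that definition. A child with a related, short, treatable Grade 3 vomiting episode in Course 1 has no DLT under 6.2.1. The same child has a non-thromboembolic toxicity under 7.1.2, is to be reduced, and so has a DLT under the first bullet of 6.2. The exemption then never operates. The same holds for milder events: nothing in 7.1.2 excludes Grade 1 nausea.

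The DLT count decides the MTD or RP2D, and the threshold is low. Once one real DLT has occurred among the first six, a single miscounted event in the other five settles the dose. The error runs towards rejecting 120 mg/m², not towards missing toxicity.

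The wording also governs treatment after Course 1. By Appendix B, reducing a child with a BSA of 0.70–1.00 m² takes the daily dose from 200 mg to 100 mg. At 80 mg/m² the literal rule ends therapy.

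**Working it through.** The plan gives no operating characteristics for the six-patient rule, so there is no figure to reproduce. The check is first textual, then an illustration of size.

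**1. Does the chain hold in the text?**

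| Event in Course 1, related | 6.2.1 / 6.2.2 | 7.1.2 literally | First bullet of 6.2 |
|---|---|---|---|
| Short Grade 3 nausea/vomiting | exempt | reduce or stop | DLT |
| Reversible Grade 3 transaminases | exempt | reduce or stop | DLT |
| Short Grade 3 fever/infection | exempt | reduce or stop | DLT |
| Correctable Grade 3 electrolytes | exempt | reduce or stop | DLT |
| Grade 4 lymphopenia | exempt | reduce or stop | DLT |
| Grade 1 nausea or fatigue | not listed | reduce or stop | DLT |

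The reduction takes effect in later cycles, but 6.2 dates the event, not the reduction, so a Course 1 event still qualifies. Superficial phlebitis, also exempted in 6.2.1 below Grade 3, stays outside the chain because 7.1.1 manages it without a dose change.

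**2. Does any other rule supply the missing threshold?** Section 6.1.2 makes unmet parameters a DLT only after 7 days, but it covers only the parameters in 3.1.9 (plus the HIV criteria in 3.1.14 where they apply). Of the five exempted types, 3.1.9 lists only ALT/AST. The reference to toxicity in 6.4.2 leads back to 6.2, whose first bullet depends on the modification rules, so it is circular. Section 7.0 speaks of criteria for reduction, but Section 7 offers none for these events except 7.1.2. The phrase dose-modifying toxicity in 6.2.4 is not defined. No sentence ranks 7.1.2 against the exemptions.

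**3. Illustration of size.** Both inputs are assumptions:

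- d = 0.10, the chance of a real DLT.
- e, the chance that a child without a real DLT has a related exempted event that is also counted as a DLT. It combines occurrence and miscounting, and is taken as independent between children.

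With no miscounting, in six children:

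- P(0) = 0.9⁶ = 0.5314
- P(1) = 6 × 0.1 × 0.9⁵ = 0.3543
- P(≥2) = 1 − 0.5314 − 0.3543 = 0.1143

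With miscounting, p = 1 − (1 − d)(1 − e) and P(≥2) = 1 − (1 − p)⁶ − 6p(1 − p)⁵. Given one real DLT, the decision tips with chance 1 − (1 − e)⁵. Given none, it tips with chance 1 − (1 − e)⁶ − 6e(1 − e)⁵.

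| e | p | P(≥2 of 6) | tips, given one real DLT | tips, given none |
|---|---|---|---|---|
| 0 | 0.100 | 11.4% | – | – |
| 0.02 | 0.118 | 15.1% | 9.6% | 0.6% |
| 0.05 | 0.145 | 21.2% | 22.6% | 3.3% |
| 0.10 | 0.190 | 32.0% | 41.0% | 11.4% |

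Check at e = 0.05: 0.1143 + 0.3543 × 0.2262 + 0.5314 × 0.0328 = 0.2118.

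**4. The fully literal rule.** If toxicity of any grade counted, a 20% rate alone would give P(≥2 of 6) = 34.5%, and a 50% rate 89.1%. Section 10.1.1 lists nausea, vomiting, fever and fatigue each at more than 20 in 100, grade not stated. A rule that would so often reject the starting dose is unlikely to be what was meant.

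**The case against.** The strongest reply is that the protocol, read as a whole, ties dose changes to DLT-type events:

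- Section 6.2.4 says that children at Dose Level 0 who have a DLT stop study therapy. That would be pointless if any toxicity at 80 mg/m² already ended treatment.
- Section 6.2.2 closes by linking Section 7 to the events just listed.
- Section 6.1.2 pairs reduction with a DLT, and lets Course 2 start on stable disease and laboratory parameters without requiring freedom from toxicity.
- Section 6.4.2 speaks of unacceptable toxicity.
- Section 6.2.4 resumes treatment at the lower dose once toxicity is back to Grade 1 or baseline, so the trigger lay above Grade 1.
- The transaminase exemption foresees restarting the drug.

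A specific exemption also normally prevails over a general phrase. The Study Chair or Co-Chair must be told before any modification (7.0), and source documents supporting DLTs are uploaded centrally (13.3).

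Most of this stands. The narrower intent is very likely, review would often put a case right, and any error is in the protective direction in a first pediatric study. What does not follow is that the text is sound. Each item is an inference, none states a threshold for 7.1.2, and reviewers have no rule for an event that is exempt in one section and reducible in another.

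A reader might infer that the trial will in fact count exempted events, or that 120 mg/m² is likely to fail for this reason. The documents do not support that. They give no Course 1 rate for related exempted events, Section 2.2.2.2 describes most related adult events as mild to moderate, and the frequencies in 10.1.1 carry no grade.

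**Conclusion.** Wrong as written; minor to moderate severity. Applied literally, 7.1.2 and the first bullet of 6.2 give a wrong DLT count and cancel five exemptions, and no sentence prevents it. This is more than missing detail, because two stated rules conflict. It is less than a design flaw, because the surrounding text makes the intended rule very likely.

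The size is unknown. The rise from 11.4% to between 15.1% and 32.0% rests on an assumed 10% real DLT rate, assumed miscount rates of 2% to 10%, independence, and reviewers who apply the literal reading. These figures show how sensitive a two-in-six rule is to a single misclassified child. They are not estimates for this trial. The cohort most exposed is one with exactly one real DLT, which at 10% is 35.4% of cohorts.

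**What to change.** In both sentences of 7.1.2, replace the bare trigger with:

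> a drug-related non-thromboembolic toxicity that meets the criteria in Section 6.2.1 or 6.2.2, or that delays treatment by > 7 days (mid-course or at the start of the next course)

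Keep the existing trigger for a next course delayed by more than 7 days, and leave the first bullet of 6.2 unchanged. Then add:

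> Events exempted in Section 6.2.1 or 6.2.2 do not by themselves require dose reduction or cessation and are not DLTs unless they delay treatment by > 7 days or therapy is reduced or stopped on clinical grounds after discussion with the Study Chair.

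The mid-course delay must be named. A reference to 6.2.1 and 6.2.2 alone would leave a related hold of more than 7 days within Course 1, a DLT under the second bullet of 6.2, with no modification rule. A reference to 6.2 as a whole would be circular.

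The cost is one phrase in two sentences and one added sentence, with no extra data or patients. Real DLTs and clinically driven reductions still count, so no safety protection is lost.
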